C. Long Term Objectives: 1) To decrease the long term risks associated with obesity such as coronary artery disease and diabetes in the SMI population. 2) To promote recovery, improve mental health, quality of life, and treatment adherence, and to decrease utilization of hospital resources by improving the overall medical and psychiatric condition of these patients. 3) To create a user-friendly intervention program that is easy to disseminate and implement and can be provided by any motivated health care provider in any mental health setting. 4) Finally, we wish to network with other mental health providers and create an educational website that will allow us to disseminate the program further outside of our 4 sites. Specifically, we think this will be helpful to ultimately disseminate this manualized long term weight loss program to other mental health programs such as PRRCs that are being established by the Uniformed Services Package throughout the country (3).

D. Hypotheses

1. Primary Hypotheses:

a) Veterans with SMI at four different sites with antipsychotic associated obesity who participate in the 12-month multi-modal, MOVE-like, intervention that includes classes of the Lifestyle Balance Program, and individualized lifestyle balance coaching, will gain more knowledge (i.e., greater change scores on before/after survey test instrument) about general health issues (e.g., nutrition, importance of exercise, etc.) than a control group receiving "usual psychiatric care."

b) Subjects randomized to active treatment in the 12-month, Lifestyle Balance Program will make more objective lifestyle changes (as measured by exit interviews, food and exercise diaries, fidelity assessments) than those in the usual psychiatric care group.

c) Subjects who participate in the 12-month multi-modal Lifestyle Balance Program will achieve better cardiovascular (e.g., sustained weight loss, better glucose tolerance, improved lipid profiles) and mental health (e.g., improvements in recovery from mental illness, improvement in biopsychosocial/spiritual wellness [measured by the WHO-QOL BREF and the BPSS], general measures of psychopathology, subjective quality of life, etc) outcomes than the control group.

2. Secondary Hypotheses:

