E. Procedures for the Usual Care Group: As most psychiatrists are being advised to counsel patients on weight, diet, and exercise, Usual Care will be only some modest counseling. Referral to the MOVE program by their treating psychiatrist would not be discouraged. Patients will be encouraged to exercise and eat a healthy diet, and will be weighed at each visit. No classes on nutrition and no exercise classes will be given to these patients as part of this program. Patients in usual care will be seen on the same schedule as the experimental group, in order to equalize contact time. At every visit, patients will complete a questionnaire about their knowledge of healthy eating habits and nutrition. After 6 months, if patients in the “usual care group” wish to participate in the more rigorous behavioral weight loss program they will be given that opportunity. A de-identified photograph of each participant’s body from the neck down will be taken during visit one and at the end of study.

SCHEDULE OF EVENTS

Visit	Time	Rater	0	1-7	8	9	10	11	12	13	14	15	16	17	18
Week			0	1-7	8	12	17	21	26	30	34	38	43	48	52
Month			0		2	3	4	5	6	7	8	9	10	11	12
Visit Log/Assessment Packet	--	--	X	X	X	X	X	X	X	X	X	X	X	X	X
AHA Exercise Risk Stratification	10	MD	X												
Brief Psychiatric Rating Scale (BPRS)	15	MD	X		X				X						X
CGI	5	MD	X		X				X						X
Hamilton Depression/ Beck Anxiety Scale	20	MD	X		X				X						X
Physical Exam	15	MD	X												X
Structured Clinical Interview for DSM-IV (SCID)	15	MD	X												
Antipsychotic Side-effects Checklist (ASC)	5	C	X		X				X						X
Assessment of Patient Food Preparation Activity	5	C	X		X				X						X
Biopsychosocial/Spiritual Wellness Self Appraisal (BPSS)	5	C	X		X				X						X
Demographics	10	C	X												

EXIT interview	5	C														X
Fidelity Checklist Change Assessment	10	Proj. Mgr	X						X							X
Framingham Hard Coronary Heart Disease	5	C	X													X
Healthy Lifestyle Balance Knowledge Quiz	15	C	X		X				X							X
Informed Consent Video	30	--	X													
Informed Consent Quiz	15	C	X						X							X
Labs: Lipid Profile, fasting glucose, HgbA1C, insulin/ HOMA calculation, c-reactive protein, microalbumin, creatinine	10	Lab	X		X				X			X				X
Lifestyle Habits Questionnaire	10	C	X	X	X	X	X	X	X	X	X	X	X	X	X	X
Motivational Interview	5	C	X		X				X							X
Quality of Life Scale	15	C	X													X
SAIQ- Insight Measure	10	C	X		X				X							X
Telephone Contact Assessment (as needed)	5	C														

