- d. We may assist the patient in finding an exercise location. The patient will be given the opportunity to take exercise classes at the VA or may be given a membership to a safe exercise facility.
- e. We may provide the patient transportation or bus fare so that the patients may attend the exercise classes.
- f. If the patient is injured or has any other physical problem, his/her exercise regimen and goal expectations may be adjusted to fit their needs.

2. Additional Dietary Interventions

- a. The patient's lifestyle coach may request to attend meals at their place of residence to observe their eating patterns and make positive suggestions.
 - b. We may provide further education to their Board and Care and/or caregivers about the importance of the patients' dietary needs.
 - c. The patient may be asked to substitute a meal or snack for a Slimfast, energy bar, or other food substitute.
 - d. The patient's dietary goals may be adjusted to a more comfortable level
 - e. The patient may be asked to repeat some classes and take additional booster sessions to relearn the material taught in class.
 - f. The patient may be reeducated about the risks and negative impact of obesity on their health.
 - g. The patient may be given take-home reminders such as pamphlets, fat counters, and other materials.
- All the additional exercise and diet interventions mentioned above are optional.

L. Minimizing Risks: Patients will be carefully examined medically and psychiatrically. Safety for exercise will be assessed and if necessary, patients may be referred for an exercise tolerance test and a monitored exercise program. If the behavioral intervention appears to be worsening psychiatric or medical symptoms patients will be discharged from the study. Specifically, patients will be discharged if their psychiatric symptoms are judged to be minimally or more worse on the CGI, from their previous visit. Patients who are observed to be gaining weight or having concerning changes in lipids, or glucose will be given any and all additional medical treatments for such metabolic changes. All additions or changes of medications to assist with metabolic changes will be recorded. No attempt to control psychiatric medication condition will be made in this study, as we wish to optimize patients' outcome. Types of drugs given will be carefully documented and examined in post hoc analyses. All usual care patients will have the option of open treatment after six months

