if in the opinion of the investigator, weight changes and/or metabolic changes warrant intervention that is more rigorous.

M. Rater Reliability: Rater reliability is maintained by all raters co-rating patients in reliability sessions. A start up meeting will include co-rating sessions to assure reliability of assessors. All psychiatric raters have undergone inter-rater reliability quality assurance testing on a yearly basis as part of their ongoing work in clinical trials research. Raters will be assigned specific patients and will be expected to rate that same patient throughout the year. Raters will be masked to randomized condition.

N. Statistics and Data Analyses

1. General Data Analysis Issues: Data Management:

A. Organization of the Data Core support ([name] Ph.D., Director, [name] senior statistician)

The multi-site study data will be managed locally at each site and will be supported by the VISN -22 MIRECC Biostatistics Core (VISN-22 MIRECC P.I. [name], M.D.) . Affiliation with the VISN-22 MIRECC Core provides the research team with expert general and specialized consultation. The Core also includes statisticians, database and MS Windows applications development programmers and other research support staff. [name] has utilized the core for other multi-site studies she has developed. Both she and her colleague, [name] in Long Beach have experience with the proposed web based data management system.

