Prior to statistical analyses, the data will be inspected to determine the advisability of scale transformation to normalize distributions or reduce variance heterogeneity (e.g., logarithmic or power transformations) and to identify missing data, outliers, or other unusual features that might bias results. Where multiple measures may overlap or be redundant, preliminary analyses will explore whether it is possible to reduce these using techniques from scale development such as factor analyses. Preliminary analyses are also performed to compare treatment groups on descriptive and clinical characteristics at baseline to ensure randomization has succeeded. If there are significant differences between the treatment groups at baseline we will create propensity scores and include them in all further analyses as covariates to compensate for potential bias. We will also test if there are significant site effects, and if necessary we will include a site variable in the mixed linear model analysis, and model time as nested in subjects and subjects nested in sites.

To address concerns about excessive Type I error rates, the principal analyses are designed to answer clearly stated major research hypotheses, and are based on well-specified dependent variables. The samples are large enough to expect that confidence limits may be reasonably narrow, and findings may be robust enough to permit conservative adjustments of p-values for multiple testing. Bonferroni and other adjustments are necessarily somewhat arbitrary as Saville notes in his argument against their use (71). Additional analyses that are exploratory will be clearly identified as such. All tests will be two-tailed at $\alpha=0.05$.

2. Attrition: Dropout from treatment does not necessarily mean participants will refuse follow-up assessments, and we will attempt to obtain full follow-up data on all enrolled participants regardless of degree of participation and include all enrolled participants in analyses when any outcome data are available (intent to treat). Attrition can compromise randomization, so preliminary analyses will compare baseline characteristics

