3. Repeated measures analyses: We propose to longitudinal (repeated measures) analyses to maximize the additional power we gain by observing the same subjects across 12 months.. Repeated measures analyses permit contrasts at each time point, and also describe and compare trajectories of change (trends), speed and durability of effects. We will also conduct separate cross-sectional to provide outcome data for ongoing safety review, interim progress reports, study oversight and conduct.

The primary design for longitudinal (repeated measures) analyses of continuous outcome scales will be a 2-group (treatment) mixed general linear model of timepoints nested within participants. This is very general linear model that permits flexibility in specifying the nature of the covariances among the dependent measures, allows time-dependent, within and between subject covariates, and permits incomplete (i.e., missing) data. Analyses of trends across the monthly assessments will be done using growth curve model within the mixed model analysis of covariance design with repeated measures described above. We propose to model a linear trend of time unless inspection clearly suggests nonlinearity. By fitting a slope over time (and intercept) for each participant who has baseline and at least one other measure, this method makes good use of all the data, and is robust even if some of the some measures are missing. The use of the mixed general linear model for all cross-sectional and linear hypotheses ensures that results will be comparable across different analyses and provide a framework to include group, person and time-specific covariates if it becomes necessary. The preliminary analyses have shown that this analysis strategy provides meaningful results even with partial data and suggests that we will exceed the originally projected power.**4. Stratification:** Randomization will be stratified by type of antipsychotic and presence of mood stabilizer medication (e.g., depakote, lithium) to assure balance on olanzapine and clozapine by randomizing within three strata – olanzapine, clozapine, and all other antipsychotics -- using three separate randomization lists. Because such stratification can adversely affect statistical power by creating artificially comparable (and heterogeneous) groups, two dummy variables coding olanzapine and clozapine at baseline will be included in all analyses as covariates.

4. Statistical Plans:

Primary Hypotheses:

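### Usual-care patients may start the program after month 6, but the primary hypotheses have no named pre-crossover contrast and no crossover-specific rule

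*Combined protocol and SAP*

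**What the plan says.** **Access.** V.E (Procedures for the Usual Care Group) says that after 6 months controls who "wish to participate in the more rigorous behavioral weight loss program they will be given that opportunity". V.L (Minimizing Risks) says "All usual care patients will have the option of open treatment after six months", and then adds the condition "if in the opinion of the investigator, weight changes and/or metabolic changes warrant intervention that is more rigorous". One passage turns on the patient's wish, the other on the investigator's judgement.

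**Hypotheses.** Primary hypothesis c (I.D) concerns a 12-month program: "Subjects who participate in the 12-month multi-modal Lifestyle Balance Program will achieve better cardiovascular" and mental health outcomes than controls.

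**Analysis.** N.2 (Attrition) will "include all enrolled participants in analyses when any outcome data are available (intent to treat"). N.3 says "We propose to model a linear trend of time unless inspection clearly suggests nonlinearity". It also notes that "Repeated measures analyses permit contrasts at each time point", without naming one. N.4 (Statistical Plans) uses baseline, 8 weeks, 6 months and 12 months, offers linear growth curves as a further option, and expects the results to inform on how well effects are maintained. For adherence only (secondary hypothesis b), N.4 commits to between-group contrasts in three epochs, two of which end by month 6.

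**Not addressed.** Section N does not mention usual-care patients who start the program, and the power section (N.5) makes no allowance for them.

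**The concern.** The last analysis visit falls after controls may have begun the treatment under test. If those who cross over benefit, the month-12 difference and the 6-12 month adherence contrast shrink. A small or null month-12 result could then mean a weak program or treated controls, and no named analysis separates the two.

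The default linear trend adds a second difficulty. Catch-up by controls after week 26 pulls down the slope difference. Because N.4 treats the repeated measures as evidence on maintenance, a narrowing gap could be reported as waning even if the program's effect is fully held.

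Three measures have no week-26 value to fall back on: the Quality of Life Scale and Framingham risk (baseline and month 12 only) and the exit interview (last visit only).

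**Working it through.** **Inputs from N.5.** 66 completers, SD 5 kg, difference 2.5 kg, within-subject correlation r = .5, m = 4 data points, two-sided alpha 0.05, f = .25 or .15. **Assumptions.** 1:1 allocation (33 per arm); equal correlation between visits; SD 5 kg at each visit; access opening after the week-26 assessment; uptake c = 10%, 30% or 50%.

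**1. The plan's own power.**
- Group effect: lambda = N f² m/(1+(m−1)r) = 66 × 0.0625 × 4/2.5 = 6.6, df 1 and 64. Power is 0.716 (plan .7199).
- Trajectories: lambda = N f² m/(1−r), df 3 and 192. At f = .25, lambda = 33.0 and power is 0.999 (plan 0.99). At f = .15, lambda = 11.88 and power is 0.828 (plan 0.83).

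The plan's figures reproduce. The group-effect scenario puts the same difference at every visit, including baseline, where randomization makes the expected difference zero. I therefore do not dilute that figure.

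**2. Month-12 difference.**
- Full catch-up: 2.5 × (1−c) = 2.25, 1.75, 1.25 kg.
- Effect building linearly, crossovers on the active slope from week 26: each gains half of 2.5 kg by week 52, so 2.5 − 1.25c = 2.38, 2.13, 1.88 kg.

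**3. Single slope on four visits (linear effect, crossovers on the active slope).** Weeks 0, 8, 26 and 52 have mean 21.5 and sum of squares 462.25 + 182.25 + 20.25 + 930.25 = 1595. The SE of the 52-week slope difference is 52 × √(2 × 25 × 0.5/(33 × 1595)) = 1.13 kg. The fitted difference is 2.5 − c × 1.25 × 52 × 30.5/1595 = 2.50, 2.38, 2.13, 1.88 kg at c = 0, 10%, 30%, 50%. Power (noncentral t, df 64) falls from 0.58 to 0.54, 0.46 and 0.37.

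The level depends on the visits used, and the plan is not consistent here: N.3 says "Analyses of trends across the monthly assessments will be done using growth curve model", while N.4 lists four assessments.

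**4. The plan's 3-df trajectory test, diluting month 12 only.** Scale a profile of differences (in SD units) so that f = √(mean squared deviation)/2 equals the plan's value without crossover. Reduce month 12 alone and recompute. Example: a linear profile at f = .25 is (0, 0.200, 0.651, 1.302). With 50% full catch-up the last value becomes 0.651, f = 0.142, lambda = 66 × 0.142² × 8 = 10.7, and power is 0.78.

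| Scenario | f=.25, 30% | f=.25, 50% | f=.15, 30% | f=.15, 50% |
|---|---|---|---|---|
| Linear, full catch-up | 0.945 | 0.78 | 0.52 | 0.34 |
| Linear, crossovers on active slope | 0.99 | 0.97 | 0.68 | 0.57 |
| Linear to week 26, then held; full catch-up | 0.99 | 0.99 | 0.70 | 0.66 |

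Steps 3 and 4 are not on the same effect. A linear profile reaching 2.5 kg at month 12 has f of only about 0.096, so f = .25 there means 2.5 × 0.25/0.096, or about 6.5 kg.

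**5. Power of a week-26 contrast.** Baseline-adjusted SE = 5 × √(1 − 0.25) × √(2/n) = 1.066 kg at n = 33 per arm and 0.791 kg at 60.
- Linear effect (1.25 kg at week 26): 0.21 and 0.35.
- Effect complete by week 26 (2.5 kg): 0.64 and 0.88.
- For comparison, month 12 with the same estimator, linear effect and 50% uptake (1.88 kg): 0.41 and 0.65.

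**The case against.** - **Delayed access is part of the comparator.** V.E places it within the usual-care procedures, so intent to treat compares the arms as designed. If crossovers benefit, dilution runs toward no difference, and a positive month-12 result stands. This is right. It limits what a null or narrowing result can mean; it does not invalidate the comparison.
- **The plan already has the tools.** N.3 permits contrasts at each visit, drops linearity if inspection clearly suggests it, and allows time-specific covariates. N.4 only considers growth curves. All true, but permission is not designation: the choice would be made after seeing the curves, and none of these provisions mentions crossover.
- **The access passages may be compatible.** They could be read jointly, as patient wish plus investigator agreement. Possibly, but neither says so; reconciliation is all that is asked.
- **The week-26 test may not settle the matter.** This stands. With a linear effect it is weaker than month 12 even at 50% uptake, and a null at week 26 would also be unclear.
- **Uptake is unknown.** This stands too, so the figures are ranges and not predictions.

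**Conclusion.** The concern holds as an inexpensive improvement that should be made. For the primary hypotheses there is no designated pre-crossover contrast, no crossover-specific rule and no sensitivity analysis. Month 12 compares the assigned program with usual care plus optional delayed access, not 12 months of program with usual care alone.

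At 10% to 50% uptake with full catch-up, the month-12 difference falls from 2.5 kg to between 2.25 and 1.25 kg. The loss could be larger if those who cross over are the controls doing worst, which the V.L condition makes plausible. For a linear effect with crossovers on the active slope, four-visit slope power falls from 0.58 to as low as 0.37. At 50% uptake the plan's trajectory power falls from 0.99 to 0.78-0.99 (f = .25) or from 0.83 to 0.34-0.66 (f = .15). All of this rests on the stated assumptions.

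A reader might infer more than the documents support:
- **That month 12 is invalid, or that post-crossover data have no rule at all.** N.2's general intent to treat would by default keep crossovers as randomized.
- **That no pre-crossover contrast exists anywhere.** Adherence has two, and the 8-week and 6-month data are unaffected by crossover.
- **That trajectory power shrinks as if all of f were multiplied by 1 minus uptake.** Weeks 8 and 26 precede crossover, so that overstates the loss.

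**What to change.** 1. In N.3 and N.4, pre-specify categorical time, or piecewise time with a knot at week 26, and state which visits enter. Name the as-randomized week-26 contrast for the primary outcomes measured then, reported beside month 12.
2. State that month-12 data are analysed as randomized. Label the month-12 contrast, the 6-12 month adherence epoch, and the measures with no week-26 value (Quality of Life Scale, Framingham risk, exit interview) as assigned program versus usual care with optional delayed access. Do not read narrowing after week 26 as waning without item 3.
3. Record each crossover date. Add one sensitivity analysis that sets control data after crossover to missing and imputes them from the usual-care trajectory, stating that crossover may depend on outcome.
4. Reconcile the access statements in V.E and V.L.

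Cost: SAP wording, one date per crossover and one extra analysis. The price is a more limited 12-month claim and a week-26 test that may have low power, which is why it sits beside month 12.

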Treatment Adherence Log	5	C	X		X				X							X
URICA Motivational Scale	10	C	X						X							X
Vitals: Weight, BMI, Waist, %Fat	10	C	X	X	X	X	X	X	X	X	X	X	X	X	X	X
Lifestyle Balance Classes	60	RD	X	X	X											
Lifestyle Balance Booster classes	60	RD				X	X	X	X	X	X	X	X	X	X	X
Personal Goal Sheet	10	RD	X	X	X	X	X	X	X	X	X	X	X	X	X	X
Eating Behavior & Exercise Adherence – additional interventions	2	RD		X	X	X	X	X	X	X	X	X	X	X	X	X
Caregiver dietary Information Session	60	RD	X			X			X			X				X
Food and Exercise Diary	15	RD	X	X	X	X	X	X	X	X	X	X	X	X	X	X
Exercise Tolerance Test	120	C	X													
Electrocardiogram	15	C	X													

Example Schedule for Lifestyle Balance Classes and Exercise Opportunities at West Los Angeles Site

Day of Week	Mon	Tue	Weds	Thurs	Fri
AM Class	Cohort 1	Cohort 2	Cohort 3	Cohort 4	Cohort 5
PM Class	Booster	Booster	Booster	Booster	Booster
Day of Week	Monday	Tuesday	Wednesday	Thursday	Friday
Exercise Options offered at PRRC:	Walking Group 11:00am Yoga 1:00pm	Physical Fitness 8:00am Yoga 1:00pm Golfing 2:00pm	Yoga 2:00pm	Thai Chi 9:00am Field Trip 10:00am (eg farmers market, museum)	Yoga 1:00pm

				walking)	
Exercise option Rehab wellness clinic	Daily available stationary bicycle and weight lifting	Daily available stationary bicycle and weight lifting	Daily available stationary bicycle and weight lifting	Daily available bicycle and weight lifting	Daily available bicycle and weight lifting

G. Study Assessments:

1. Screening and General Medical Procedures: The process of obtaining informed consent will culminate in a quiz on the details of the project and participating in research, which is repeated at 6 and 12 months. During the first visit, patients will have a comprehensive physical exam and psychiatric interview. An electrocardiogram and demographics will be recorded. Framingham risk assessment for cardiovascular disease will be calculated and repeated at the end of the study. Routine vital signs, blood pressure, and pulse will be measured at each visit. Patients at high risk for cardiovascular disease and/or current symptoms of angina may need referral for an exercise tolerance test before embarking upon the exercise component of this behavioral weight loss program. [name], our co-investigator in charge of the outpatient rehabilitation medicine department, has agreed to assist us with expediting exercise tolerance tests for patients wishing to participate in exercise as part of their weight loss plan.

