H. Adherence Methods: Each patient will be assigned a lifestyle balance coach/case manager. The model we use in our treatment of patients is intensive case management and a minimum of bimonthly contacts for each patient. Patients assigned to the "usual care" group will also have case managers and equal contact so that contact time will be equal for each group. We have had extensive experience with utilizing a case management approach with all of our previous clinical trials, and successfully used during our current merit review program. The diabetes prevention program that has been adapted for this protocol has an extensive operations manual that has a long section devoted to methods of improving adherence to the Lifestyle Balance program. Please see appendix of this grant for our operations manual and particularly the "toolbox" section for helping patients adhere to the Lifestyle Balance program.

Adherence is dependent, in part, on environmental and caregiver influences. Many of our patients have little influence over the food that is fed to them in board and care homes. We will assess patient's involvement in food preparation and their willingness to involve their caregivers in helping make necessary dietary changes. Our Lifestyle Balance coaches will act as a liaison to patients' caregivers, family, and or board and care operators and will provide on-site nutritional and cooking education and to assist these care providers with understanding the dietary needs of the patients involved with our behavioral program. In some cases, we may need to recommend meal replacements such as Slimfast when patients are having difficulty with portion control. Patients' participation in their own food preparation will be assessed initially as well as their willingness to have us contact their caregivers to provide support and education towards the dietary goals of this program. Our patients will be asked to provide a food and exercise diary. If patients are having difficulty with losing weight, they will be asked if they would be willing to allow a case manager to attend their meals for a few days to assist them in making healthy choices.

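### The plan says contact time is equal in both arms, but it matches only the number and timing of visits; the scheduled class time alone leaves a gap of about 14 to 15 hours net over 12 months

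*Combined protocol and SAP*

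**What the plan says.** Equal contact time appears twice as a feature of the design. Section V.E (Procedures for the Usual Care Group) says: "Patients in usual care will be seen on the same schedule as the experimental group, in order to equalize contact time". Section V.H (Adherence Methods) adds that usual-care patients have case managers and "equal contact so that contact time will be equal for each group".

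Section V.E also limits what usual care contains: "Usual Care will be only some modest counseling", and "No classes on nutrition and no exercise classes will be given to these patients as part of this program". Its one listed activity that can be given a length is a knowledge questionnaire at every visit.

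The Schedule of Events lists visits 0 to 18. It allots 60 minutes to the row "Lifestyle Balance Booster classes" and 60 minutes to the initial class row, both delivered by the dietitian. Together these rows cover every visit. Section V.D places the classes, diaries, individual goal-setting and caregiver meetings among the procedures for patients randomized to the program.

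**The concern.** A shared visit calendar equalizes time only if a visit lasts equally long in both arms. Here one arm has an hour of class at each visit and the other has modest counseling of unstated length.

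This bears mainly on the mental-health part of primary hypothesis (c) in section I.D: psychopathology, quality of life and biopsychosocial/spiritual wellness. The wellness scale is a self-report, and the trial is open to patients. Masked raters protect against rater bias, but not against an effect of extra staff time on how the patient feels. Section V.I describes staff contact in the program as deliberately reinforcing, with affirmation for attendance itself. A reader told that contact time was equal would set aside added attention as an explanation for a difference on these outcomes. The design does not support doing so.

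**Working it through.** **The plan's figure.** The stated difference in contact time is zero. The schedule does not reproduce it.

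**Inputs**
- Visits: 0, 1–7, 8 and 9–18, so 1 + 7 + 1 + 10 = 19 (Schedule of Events).
- Initial classes: 60 min at visits 0, 1–7 and 8, so 9 class visits (Schedule of Events). The narrative gives 16 classes at two per session, once a week for 8 weeks, so 8 sessions (V.D.6 and V.D.7).
- Boosters: 60 min at visits 9–18, so 10. The row shows one more mark than there are visits in the text available to me; this looks like a table-extraction artefact, and I used 10. V.D.7 mentions 16 months, but I used the 12 months of the schedule.
- Knowledge questionnaire: 15 min (Schedule of Events); 4 occasions in the program arm (V.D.5) and every visit in usual care (V.E). I assume that the usual-care questionnaire also takes 15 min.
- Usual-care counseling and case-manager contact: no minutes given in either arm, so not counted.

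**Class time, program minus usual care, 12 months**
- Narrative: (8 + 10) × 60 = 1,080 min = 18 h.
- Schedule: (9 + 10) × 60 = 1,140 min = 19 h.
- Extra usual-care questionnaires: (19 − 4) × 15 = 225 min = 3.75 h.
- Net: 18 − 3.75 = 14.25 h, or 19 − 3.75 = 15.25 h.

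If each of the 16 classes took its own 60 minutes, the gross figure would be 16 + 10 = 26 h. I do not rely on that reading, because the schedule gives 60 minutes per class visit.

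**By month 6 (visit 12), before usual-care patients may enter the program**
- Schedule: 9 classes + 4 boosters = 13 h gross.
- Narrative: 8 + 4 = 12 h gross.
- Extra questionnaires: (13 − 3) × 15 = 150 min = 2.5 h, so 10.5 h or 9.5 h net.

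**All dietitian-delivered rows, 12 months**

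| Row | Minutes |
|---|---|
| Classes and boosters | 1,140 |
| Personal goal sheet, 10 × 19 | 190 |
| Eating and exercise adherence, 2 × 18 | 36 |
| Caregiver session, 60 × 5 | 300 |
| Food and exercise diary, 15 × 19 | 285 |
| Total | 1,951 (32.5 h) |

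Net of the questionnaires this is 32.5 − 3.75 = 28.8 h. A cautious version takes 8 class sessions, drops the caregiver and diary rows, and nets the questionnaires: 1,080 + 190 + 36 − 225 = 1,081 min, about 18.0 h.

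**The case against.** **The plan never claims to separate program content from attention.** A reader might infer such a claim from the stated aim of equalizing contact time. The documents do not make it. The objectives and hypotheses compare a multi-modal program with usual psychiatric care in an open effectiveness trial, and the analysis plan makes no use of contact time. This stands: the defect is a false description of the design, not a flaw in the comparison.

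**Section V.H may mean case-manager contact only.** The sentence follows one on intensive case management, and the classes are run by the dietitian. That reading is possible, and it would make V.H ambiguous rather than wrong. It does not rescue V.E, which offers the shared visit schedule as the means of equalizing time. Nor are minutes or content given for case-manager contact that could offset the classes.

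**Nineteen hours is not a floor.** A reader of the schedule might take it as a minimum. It falls to 18 h on the narrative, and to 14 to 15 h net of questionnaires. It is smaller again for usual-care patients who take up the program after 6 months. This stands.

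**The 32.5 h total is softer.** The schedule is not split by arm. Caregiver meetings concern patients who do not prepare their own food and who agree. Diaries are named as a measure of lifestyle change between arms, so that row might apply to both, although V.D.4 names only the program arm. This also stands, so 32.5 h is an upper figure on the schedule's counts.

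**No estimate, test or sample size changes.** Correct.

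**Conclusion.** The point holds as a correction to a stated design property. Visit number and timing are matched; contact time is not. Scheduled class time differs by 18 to 19 h gross, or about 14 to 15 h net of the extra questionnaires, over 12 months. By month 6 the gap is about 13 h gross on the schedule. Counting every dietitian row gives up to about 32.5 h.

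These are planned durations. They assume full attendance, that usual-care patients stay in usual care for the 12-month figures, and that the unquantified counseling and case-manager time does not favor usual care by a similar amount. Nothing in the documents suggests that it does.

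The documents give no estimate of how far extra attention moves the mental-health, quality-of-life or wellness scores, so no bias can be sized. What is lost is the right to call these outcomes contact-matched. The whole-package comparison with usual care remains valid.

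**What to change.** 1. In V.E and V.H, replace the equal-contact statements with wording such as: *The number and timing of scheduled visits are the same in both arms; contact time is not, because the Lifestyle Balance arm receives classes and related sessions.* If V.H is meant to cover case-manager contact only, say so.
2. State in V.N that the comparison, including the mental-health, quality-of-life and wellness outcomes, is of the whole package (with its added staff attention) against usual care, and will not be described as contact-matched.
3. Mark in the Schedule of Events which rows apply to which arm, and reconcile the 8 class sessions of the narrative with the 9 class visits of the schedule.
4. Report, by arm and beside those outcomes, scheduled contact time and the visits and classes attended, showing separately the usual-care patients who entered the program after 6 months.

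A reader might assume that minutes per visit are already logged. The documents do not say so: the visit-log row carries no duration, and V.I provides for tallying the number and types of interventions, not time. Item 4 therefore uses scheduled time and attendance. Actual minutes would need new data collection, which is not required here.

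The cost is wording and one descriptive table, provided class attendance is recorded. Neither arm changes. The small downside is a weaker attribution claim for these outcomes.
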